The MLC spinal anesthesia protocol included 500cc of isotonic crystalloid solution for vascular filling, bupivacaine 7 to 10 milligrams (depending on the patient's height), morphine 100 micrograms, and sufentanil 10 micrograms.

The FAUCS spinal anesthesia protocol included no vascular filling, no morphine, bupivacaine 7 to 10 mg (depending on the patient's height), and sufentanil 10 micrograms.

A bladder catheterization was performed on the MLC group by using a 16 or 18-F catheter prior to the skin incision. In both groups, a single dose of a first-generation cephalosporin was administered intravenously.

All FAUCS surgeries were performed by two senior surgeons ([name] and [name]). Both were experienced with the paravesical approach and had performed more than 30 cases previously. The MLC cesarean operations were performed by same seniors or residents who performed vast majority of the operations in the unit.

For this study, we performed the MLC technique as described in 1999 ³.Regarding the FAUCS approach described in 2017, the use of skin glue for closure is recommended ⁶. In order to

ensure that all the patients were virtually indistinguishable, we alternatively employed a subcuticular absorbable Vicryl suture for the skin closure.

Hematocrit levels were assessed before and after surgery. Analgesics were administered by the nursing staff, upon patient's requests and visual analogue scale (VAS)⁸. Assessments with VAS were made every 6 hours: H0,H6,H12,H18, and H24. A standardized analgesics scheme was used:

First intention: 100 mg Ketoprofen intra-rectal route every 6 hours.

Second intention: intra venous1g paracetamol every 6 hours.

Third intention: tramadol 50 mg oral route every 6 hours.

A first standing was proposed to all women everyhour during the first post operative day.

The bladder catheter was removed as soon as the woman was able to walk alone.Normal oral food intake was initiated as soon as gas passage occurred and the patient felt hungry.

Women were evaluated by the end of the first day. If there were no complications and if the patient felt autonomous and pain-free, they were discharged 24 hours after the surgery. In the other cases, patients were discharged at least 48 hours after surgery after a similar evaluation of maternal autonomy.

The primary outcome measure of the study was the post-operative mean pain score (PMPS).

PPMS = (VAS H0+ VAS H6 + VAS H12+ VAS H18 + VAS H24)/5.

Secondary Outcome Measures were:

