We measured 44 outcome variables. The metrics were grouped into four categories: surgery, overall morbidity, neonatal outcomes and maternal autonomy during recovery. All the analyses were conducted in RStudio (version 3.5.1). We performed unequal variance t-tests for all continuous variables and evaluated each distribution for normality using the Shapiro Wilk test. Continuous variables were analyzed with the student's t test and Mann-Whitney test. We performed asymptotic generalized Pearson's chi-squared tests for the categorical variables. When the categorical variables were ordinal, we used the Cochran-Armitage test, comparing one ordinal variable with a dichotomous one. All tests were performed as 2-tailed tests, and $p < .05$ was accepted as statistically significant.

To visualize the results, we employed smoothed kernel density plots of continuous outcome variables for FAUCS compared with the MLC values, which were viewed on a log scale where applicable.

5. S BD, J C. Extraperitoneal versus transperitoneal cesarean section in surgical morbidity in a tertiary care centre. *Int J ReprodContraceptObstet Gynecol.* 2017 Jul 26;6(8):3397–9.

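### One unadjusted p<.05 rule covers all 44 outcome variables although only PMPS is primary; a lesser point is that the deciding test for PMPS is left open

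*Combined protocol and SAP*

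**What the plan says.** The Combined protocol and SAP names PMPS, the average of five VAS readings from H0 to H24, as its single primary outcome. It then opens a list with "Secondary Outcome Measures were". The sample-size paragraph under Statistics is built on PMPS only.

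The test paragraph under Statistics states "We measured 44 outcome variables" and sorts them into four categories. It closes with one rule for every test: two-tailed, with p below .05, which "was accepted as statistically significant". The document gives no adjustment, testing order, gatekeeping or exploratory label for the non-primary outcomes.

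On the choice of test, the same paragraph says "We performed unequal variance t-tests for all continuous variables" and that the authors "evaluated each distribution for normality using the Shapiro Wilk test". The next sentence has continuous variables analysed with the Student's "t test and Mann-Whitney test". Nothing links a Shapiro-Wilk result to a choice between them. Categorical variables get Pearson "chi-squared tests for the categorical variables", and ordinal ones get Cochran-Armitage.

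**The concern.** There are two issues, of unequal weight.

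**Main issue: the non-primary outcomes.** The plan separates primary from secondary, but its significance rule does not. A difference in operating time, morbidity, neonatal condition or recovery with p just under .05 would be declared significant on the same terms as PMPS. With this many outcomes, some such results are expected by chance alone, and one could be reported as a real advantage of one technique.

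**Lesser issue: the deciding test.** One sentence gives the unequal-variance (Welch) t-test to all continuous variables, PMPS included. The next names Student's t and Mann-Whitney. Student's may be a loose label for the t-test, and Student versus Welch makes no practical difference here. The choice between t-test and Mann-Whitney is open, so the text allows more than one p-value for the primary outcome.

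**Working it through.** The plan gives no figure of its own for multiplicity or for the test choice, so there is none to reproduce.

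**Inputs from the document.** 44 outcome variables; two-tailed .05 for all tests; 50 per group; PMPS mean 3.8 and SD 2; planned decrease 60%, so 0.6 × 3.8 = 2.28 points.

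**Count of named secondaries (mine, with cord blood gases counted once).** VAS maximum 1, analgesic dose 1, blood loss 1, T1 to T4 4, incidents 4, autonomy 3, newborn 6, discharge 1: total 21. Binary: 4 incidents + neonatal hospitalization = 5. Non-binary: 21 − 5 = 16.

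**Expected chance findings, upper figure.** 44 − 1 = 43 non-primary outcomes; 43 × 0.05 = 2.15 if all are null and each is tested once at exactly 5%.

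**Allowance for rare events.** Pearson chi-squared rejects less often than 5% when events are rare. Its exact null size is the sum, over all pairs of event counts, of Bin(x₁; 50, p) × Bin(x₂; 50, p) where the test gives p<.05. Without continuity correction this is 0.0019, 0.0130 and 0.0434 at assumed event rates of 1%, 2% and 5%. With m outcomes, k of them binary, the expected number is (m − k) × 0.05 + k × size:

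| m | k | 1% | 2% | 5% |
|---|---|---|---|---|
| 43 | 5 | 1.91 | 1.97 | 2.12 |
| 43 | 15 (assumed) | 1.43 | 1.60 | 2.05 |
| 21 | 5 | 0.81 | 0.87 | 1.02 |

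For example, the last entry is 16 × 0.05 + 5 × 0.0434 = 1.02. True differences lower these: if only 22 outcomes were null, 22 × 0.05 = 1.1.

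**Chance of at least one.** If independent, 1 − 0.95^38 = 0.86 for the 43 − 5 = 38 others, and 1 − 0.95^16 = 0.56 for the 16 named. With equally correlated normal statistics (200,000 simulated runs) at assumed correlations 0.3, 0.5 and 0.7, the figures are 73%, 56% and 37% for 38 outcomes, and 47%, 37% and 27% for 16.

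**Choice of test for PMPS.** Simulation at 50 per group, mean 3.8, SD 2. The VAS-like model averages five rounded scores on an assumed 0–10 scale, with an assumed within-patient SD of 1.5.

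- Null, either Welch or Mann-Whitney below .05 (20,000 runs): 5.8% VAS-like, 5.9% normal, 6.2% gamma. A separate rerun gave about 5.4%.
- Null, test chosen by Shapiro-Wilk (10,000 runs): 5.2%, 5.3% and 5.2%. The Monte Carlo standard error is √(0.052 × 0.948 / 10,000) = 0.2 points, so no clear inflation.
- Verdicts differ in 3.6%, 6.1% and 3.7% of VAS-like trials at assumed true effects of 0.4, 0.8 and 1.2 points, and in about 0.01% at 2.28. At 0.8 points Welch power is about 50%, so that is near the worst case.

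**The case against.** **PMPS is protected.** There is one named primary, the trial is sized on it, and the rest are called secondary; some would say that is label enough. This stands for the primary: a reader might infer that 44 tests inflate the error rate of the PMPS comparison, and they do not. It does not answer the rule itself, which grants significance to every outcome on equal terms.

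**The counts are upper figures.** Several outcomes are unlikely to be null by design. Only the MLC group has bladder catheterization, spinal morphine and vascular filling, which bear on urination, standing, pain and analgesic use. Chance findings favouring one given technique are about half of the two-sided counts (0.81 / 2 = 0.4 to 2.15 / 2 = 1.1). Apgar scores and discharge in days are coarse, so 5% per test is approximate. The independent-case 86% is unrealistic if components of PMPS are among the 44. All of this stands, which is why the claim is up to about two.

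**About half of the 44 look unnamed.** A reader might subtract 1 + 21 = 22 from 44 and infer this. The documents do not support it. They also name five VAS time points, two hematocrits, percent blood volume lost and three analgesics: 5 + 2 + 1 + 3 = 11, giving 22 + 11 = 33. They do not say which of these belong to the 44, nor that all 44 are separate hypothesis tests.

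**A t-test is the natural primary reading.** Welch is assigned to all continuous variables and the sizing uses a mean and SD. This is fair, and it makes the second issue a clarification.

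**The test may have been picked after seeing results.** A reader might infer this from the past tense, the study period ending January 2019 and a reference accessed on 21 April 2019. These show only that this version was edited after that period. The documents do not say whether results had been seen.

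**Conclusion.** The concern holds at modest weight; the plan should be changed. The significance rule gives every non-primary outcome the same standing as PMPS, and up to about two of them could be called significant by chance. That rests on all 43 being null and separately tested; on the named secondaries alone the figure is about one. The event rates and correlations used are assumptions.

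The open choice of test for PMPS is a real gap but a small one. Type I error would be about 5.4 to 6.2% if either test counted as success, and about 5.2% under a normality-gated rule, which is a plausible reading but is not written. These figures rest on the planning mean and SD and on assumed shapes. At the planned 2.28 points the two tests almost never disagree; the choice matters only if the true effect is well below that.

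**What to change.** 1. State that the only confirmatory claim is PMPS at two-sided 0.05.
2. Report all other outcomes as exploratory, with estimates, 95% CIs and p-values labelled unadjusted. A Holm or false-discovery-rate adjustment is optional for any secondary the sponsor wants to claim. Safety incidents stay unadjusted so that harm signals are not hidden.
3. Rewrite, rather than delete, the sentence naming Student's t and Mann-Whitney, because it is the only mention of Mann-Whitney. It should say that the unequal-variance t-test already named is the deciding analysis for PMPS, with mean difference and 95% CI, and the main analysis for the other continuous outcomes, whatever Shapiro-Wilk shows. Mann-Whitney becomes a sensitivity analysis. A fixed Mann-Whitney would also close the gap; Welch is proposed because the plan names it first and for all continuous variables.
4. If data have been seen, disclose that the choice of test is post hoc and show both p-values.

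This is wording only and needs no new data. The costs are that fewer secondary results can be called significant, and that a test fixed now may have to be declared post hoc.
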